8.5 Outliers

Descriptive statistics will be used to identify potential outliers in key variables and/or parameters. Suspected outliers will be included in all analyses unless there is sufficient scientific justification to exclude them.

8.6 Distributional Characteristics

The assumptions underlying the proposed statistical methodologies will be assessed as appropriate. Data transformations or alternative non-parametric methods of analyses will be utilized should there be a requirement.

8.7 Validation of Statistical Analyses

Programs will be developed and maintained, and output will be verified in accordance with current risk-based quality control procedures.

Tables, figures, and listings will be produced with validated standard macro programs where standard macros can produce the specified outputs.

The production environment for statistical analyses consists of Amgen-supported versions of statistical analysis software; for example, the SAS System version 9.4 or later.

9. Statistical Methods of Analysis

9.1 General Considerations

Analyses will be split by study part and group (for part 2 only) unless otherwise specified

Descriptive statistics will be provided for selected demographics, exposure, safety, PK, efficacy data. Descriptive statistics on continuous data will include means, medians, standard deviations and ranges, while categorical data will be summarized using frequency counts and percentages. Graphical summaries of the data may also be presented. Confidence intervals (CI) for proportions will be estimated using an exact method proposed by Clopper-Pearson (Clopper and Pearson, 1934). Kaplan-Meier methods will be used to estimate the median and percentiles for time to event endpoints with CI calculated using the Brookmeyer and Crowley (Brookmeyer and Crowley, 1982) method. Kaplan-Meier methods will be used to estimate landmarks for time to event endpoints (e.g., 1-year overall survival [OS]) with the Greenwood formula (Kalbfleisch and Prentice, 1980) used to estimate the standard error used in CI calculation.

9.2 Subject Accountability

The number and percent of subjects who were enrolled, received investigational product, completed investigational product, discontinued from investigational product (including

Date: 24 March 2023 Page 33 of 53

reasons for discontinuation), completed study, discontinued the study (including reasons for discontinuation) will be summarized. Key study dates for the first subject enrolled, last subject enrolled, and last subject's end of study will be presented.

9.3 Important Protocol Deviations

Important Protocol Deviations (IPDs) categories are defined by the study team before the first subject's initial visit and updated during the IPD reviews throughout the study prior to database lock. These definitions of IPD categories, subcategory codes, and descriptions will be used during the course of the study. Eligibility deviations are defined in the protocol. The final IPD list is used to produce the summary of IPDs table and the list of Subjects with IPDs. In addition, a separate listing of all inclusion and exclusion deviations will be provided.

9.4 Demographic and Baseline Characteristics

The following descriptive summaries of the demographic and baseline characteristics will be produced:

- Race (White, Asian, Black or African American, and other categories depending on frequency observed). If multiple races have been reported for a subject, the subject will be categorized as 'Multiple'.
- Ethnicity (Hispanic or Latino, Not Hispanic or Latino) for subjects reporting
 'White' race
- Sex (Female, Male)
- Age at enrollment in years
- ECOG performance status at baseline (0, 1, 2, 3, 4)
- Weight (kg)
- Height (cm)
- BMI (kg/m²)
- Time from initial diagnosis to enrollment (months)
- Histopathology type (Adenocarcinoma, Small cell neuroendocrine prostate cancer,
 Prostate cancer with neuroendocrine differentiation, Other)
- Prior lines of therapy (0, 1, 2, 3, >=4)
- Prior radiotherapy for current malignancy (Yes, No)
- Prior surgery for current malignancy (Yes, No)

Date: 24 March 2023 Page 34 of 53

- Metastatic (Yes, No)
- Number of metastatic sites (0,1, 2, >=3)
- Brain metastases (Yes, No)
- Liver metastases (Yes, No)
- Bone metastases (Yes, No)
- Sum of diameters of target lesions at baseline based on investigator assessment (mm)
- •

Date: 24 March 2023 Page 35 of 53

9.5 **Efficacy Analyses**

The following efficacy analysis will be performed.

9.5.1 **Analyses of Primary Efficacy Endpoint(s)/Estimand(s)**

Not applicable for this study.

9.5.2 **Analyses of Secondary Efficacy Endpoint(s)/Estimand(s)**

For the primary analysis, central reviewer data when available will be used for the following secondary efficacy endpoints: objective response per RECIST 1.1, duration of response per RECIST 1.1, disease control rate per RECIST 1.1 and radiographic progression-free survival per RECIST 1.1 with PCWG3 modifications. Local investigator data may also be used for primary analysis if deemed necessary.

Analyses of **s**econdary **e**fficacy **e**ndpoints are defined in the Table 9-1.

Table 9-1. Secondary Efficacy Endpoint Summary Table

Endpoint	Statistical Analysis	Analysis Set
Objective response (OR) per RECIST 1.1	The proportion of subjects with an OR will be summarized along with the Clopper-Pearson (Clopper and Pearson, 1934) exact 95% CI.	Local data: RECIST 1.1 Evaluable by Investigator Assessment Analysis Set; Central data: RECIST 1.1 Evaluable by Central Reviewer Analysis Set
Duration of response (DOR) per RECIST 1.1	The distribution of DOR, including the median and percentiles will be summarized using the Kaplan-Meier (KM) method with CI calculated using the Brookmeyer and Crowley (Brookmeyer and Crowley, 1982) method. Landmarks at the selected time points (e.g. 3, 6, 9 and 12 months) will be reported along with	Local data: RECIST 1.1 Evaluable by Investigator Assessment Analysis Set; Central data:

Product: Tarlatamab (AMG 757) Protocol Number: 20200040 Date: 24 March 2023

Page 36 of 53

Endpoint	Statistical Analysis	Analysis Set
	95% CI using the Greenwood formula	RECIST 1.1
	(Kalbfleisch and Prentice, 1980) to estimate the	Evaluable by
	standard error in CI calculation.	Central
		Reviewer
		Analysis Set
Radiographic	The distribution of rPFS, including the median	Interim: Interim
progression-free	and percentiles will be summarized using the	Efficacy
survival (rPFS) per	Kaplan-Meier (KM) method with CI calculated	Analysis Set
RECIST 1.1 with	using the Brookmeyer and Crowley	Primary/Final:
PCWG3	(Brookmeyer and Crowley, 1982) method.	Safety
modifications	rPFS rate at the selected time points (e.g. 3, 6,	Analysis Set
	9 and 12 months) will be reported along with	7
	95% CI using the Greenwood formula	
	(Kalbfleisch and Prentice, 1980) to estimate the	
	standard error in CI calculation.	
Overall survival	The distribution of OS, including the median	Interim: Interim
(OS)	and percentiles will be summarized using the	Efficacy
	Kaplan-Meier (KM) method with CI calculated	Analysis Set
	using the Brookmeyer and Crowley	Primary/Final:
	(Brookmeyer and Crowley, 1982) method. OS	Safety
	rate at the selected time points (e.g. 3, 6, 9 and	Analysis Set
	12 months) will be reported along with 95% Cl	7 triary 515 CCt
	using the Greenwood formula (Kalbfleisch and	
	Prentice, 1980) to estimate the standard error	
	in CI calculation.	
Disease c ontrol	The proportion of subjects with disease control	Local data:
rate (DCR) per	(i.e. a BOR of CR, PR or SD) with	RECIST 1.1
RECIST 1.1	corresponding exact 95% CI will be calculated	Evaluable by
	using the Clopper-Pearson (Clopper and	Investigator
	Pearson, 1934) method.	Assessment
		Analysis Set;
		Central data:

Product: Tarlatamab (AMG 757) Protocol Number: 20200040 Date: 24 March 2023

Page 37 of 53

Endpoint	Statistical Analysis	Analysis Set
		RECIST 1.1
		Evaluable by
		Central
		Reviewer
		Analysis Set

[figure not shown]

Table 9-2. Exploratory Efficacy Endpoint Summary Table

Endpoint	Statistical Analysis	Analysis Set

Product: Tarlatamab (AMG 757) Protocol Number: 20200040 Date: 24 March 2023

Date: 24 March 2023 Page 38 of 53

Endpoint	Statistical Analysis	Analysis Set

Product: Tarlatamab (AMG 757) Protocol Number: 20200040 Date: 24 March 2023

Date: 24 March 2023 Page 39 of 53

Endpoint	Statistical Analysis	Analysis Set

Product: Tarlatamab (AMG 757)
Protocol Number: 20200040
Date: 24 March 2023
Page 40 of 53

9.6 Safety Analyses

9.6.1 Analyses of Primary Safety Endpoint(s)

Analyses of Primary Safety Endpoints are defined in the Table 9-3.

Table 9-3. Safety Endpoint Summary Table

		Analysis
Endpoint	Statistical Analysis	Set
DLT	A listing and summary of the subject incidence of DLT will be provided.	DLT Analysis Set
TEAE	The subject incidence of adverse events will be summarized for all TEAEs, TRAEs, serious TEAEs, grade 3 or above TEAEs, fatal TEAEs, TEAEs leading to withdrawal of investigational product, TEAEs leading to interruption of investigational product.	Safety Analysis Set
Vital Signs	Summary of non-missing sample size (n), mean, standard deviation, median, minimum, and maximum for continuous data will be estimated for absolute and change from baseline data.	Safety Analysis Set
ECG	No statistical analysis is planned.	
Lab	Summary of non-missing sample size (n), mean, standard deviation, median, minimum, and maximum for continuous data will be estimated for absolute and change from baseline data. Frequencies and percentages for categorical data will be reported. Shifts in grades of safety laboratory values between the baseline and the worst on-study value will be tabulated. Potential Hy's Law cases will be summarized.	Safety Analysis Set

Date: 24 March 2023 Page 41 of 53

9.6.2 Adverse Events

The Medical Dictionary for Regulatory Activities (MedDRA) version 25.0 or later will be used to code all events categorized as adverse events to a system organ class and a preferred term.

The subject incidence of adverse events will be summarized for all TEAEs, TRAEs, serious TEAEs, grade 3 or above TEAEs, fatal TEAEs, TEAEs leading to withdrawal of investigational product, TEAEs leading to interruption of investigational product.

Subject incidence of all TEAEs, TRAEs, serious TEAEs, grade 3 or above TEAEs, fatal TEAEs, and TEAEs leading to withdrawal and interruption of investigational product or other protocol-required therapies will be tabulated by system organ class and preferred term in descending order of frequency. Where appropriate the tables will also be presented by worst grade. The severity of each adverse event will be graded using CTCAE version 4.0. The above AE tables will not be created if two or fewer subjects experience the AE.

Subject incidence of events of interest (standardized MedDRA queries and/or Amgen Medical Queries) will also be summarized according to their categories and preferred term.

9.6.3 Laboratory Test Results

Laboratory data will be summarized using standard descriptive statistics at each scheduled time point in the study. Summaries of the absolute value and/or changes from baseline at each scheduled assessment will be provided for selected laboratory parameters of interest.

Shift tables indicating the change between the baseline and the maximum post dose CTCAE grades for an increased value, and the maximum post dose grade for a decreased value will be provided for selected laboratory parameters of interest. Unscheduled assessments will be included in the shift tables.

The subject incidence of potential cases of Hy's Law will be summarized. Hy's law cases have the following three components: 1) ALT or AST > 3 X ULN, 2) ALP < 2 X ULN and 3) TB \geq 2 X ULN, on any day. A listing of AST, ALT, and Total Bilirubin values at each time point may be produced for the subjects suspected of fulfilling the criteria for Hy's law.

Date: 24 March 2023 Page 42 of 53

9.6.4 Vital Signs

Vital signs data will be reviewed for each subject. Depending on the size and scope of the changes, the analyses of vital signs may include summary statistics over time and/or changes from baseline over time.

Shifts in scores for ECOG performance status between the baseline and each assessed post-baseline timepoints will be tabulated. ECOG performance status scores will be summarized at relevant time points.

9.6.5 Physical Measurements

The analysis of physical measurements will include summary statistics at baseline.

9.6.6 Electrocardiogram

The ECG measurements are performed as per standard of care for routine safety monitoring, rather than for assessment of potential QTc effect. No statistical analyses of ECG measurements are planned.

9.6.8 Exposure to Investigational Product

Subject exposure to tarlatamab will be summarized using descriptive statistics. Descriptive summary will be provided for **number of doses**, cumulative dose (mg), relative dose intensity (%) and **treatment** duration (weeks).

Listing of the unique manufacturing lot numbers, and a listing of the subjects administered each manufacturing lot number will be provided.

9.6.9 Exposure to Non-investigational Product

Not applicable for this study.

9.6.10 Exposure to Other Protocol-required Therapy

Descriptive statistics may be produced to summarize the exposure to dexamethasone 8 mg IV (or equivalent dose of other corticosteroids) and/or Prophylaxis with IV hydration 1 L normal saline.

Date: 24 March 2023 Page 43 of 53

9.6.11 Exposure to Concomitant Medication

The number and proportion of subjects receiving concomitant medication will be summarized by preferred term or category as coded by the World Health Organization Drug (WHO DRUG) dictionary.

9.7 Other Analyses

The following additional analyses will be performed.

9.7.1 Analyses of Pharmacokinetic or Pharmacokinetic/Pharmacodynamic Endpoints

For tarlatamab, PK parameters will be determined from the time concentration profile using standard non-compartmental approaches and considering the profile over the complete sampling interval. Based on the review of the data, exploratory analyses to describe the relationship between tarlatamab exposure and either PD effect and/or clinical outcome may also be performed. These exploratory analyses may not be part of the clinical study report.

[figure not shown]
9.7.2 Analyses of Clinical Outcome Assessments

Not applicable for this study.

9.7.3 Analyses of Health Economic Endpoints

Not applicable for this study.

9.7.4 Analyses of Biomarker Endpoints

9.7.5 Analyses for COVID-19 Impact

Impact of COVID-19 on study conduct and patient safety may be analyzed as per the guidelines in GDE-409220 if applicable.

Date: 24 March 2023 Page 44 of 53

10. Changes From Protocol-specified Analyses

Protocol section 9.3.1 mentions interim efficacy analysis to be performed using Interim Efficacy Analysis Set. But the interim efficacy analysis will be performed using RECIST 1.1 Evaluable by Investigator Assessment Analysis Set and RECIST 1.1 Evaluable by Central Reviewer Analysis Set for local data and central data respectively for the following endpoints: objective response per RECIST 1.1, duration of response per RECIST 1.1 and disease control rate per RECIST 1.1.

11. Literature Citations / References

12. Prioritization of Analyses

There is no prioritization of analyses.

13. Data Not Covered by This Plan

Exploratory data not included in this plan may be analyzed at a later date or by a different Amgen department.

Date: 24 March 2023 Page 45 of 53

14. Appendices

Appendix A. Imputation Rules for Partial or Missing Dates for Adverse Events, Concomitant Medications and Death

The start and stop dates for adverse events, concomitant medications and death will be imputed using the following algorithm:

Table 14-1. Imputation Rules for Partial or Missing Start Dates

		Stop Date						
		Complete: yyyymmdd		Partial: yyyymm		Partial: yyyy		
Start Dat	te	< 1 st dose	≥ 1 st dose	< 1 st dose yyyymm	≥ 1 st dose yyyymm	< 1 st dose yyyy	≥ 1 st dose yyyy	missing
Partial: yyyymm	= 1 st dose yyyymm	2	1	2	1	n/a	1	1
	≠ 1 st dose yyyymm		2		2	2	2	2
Partial:	= 1 st dose yyyy	3	1	3	1	n/a	1	1
	≠ 1 st dose yyyy		3		3	3	3	3
Missing		4	1	4	1	4	1	1

^{1 =} Impute the date of first dose

Note: For subjects who were never treated (first dose date is missing), partial start dates will be set to the first day of the partial month.

Note: If the start date imputation leads to a start date that is after the stop date, then do not impute the start date.

Imputation rules for partial or missing stop dates:

- For partial stop date mmyyyy, impute the last of the month.
- For partial stop date yyyy, impute December 31 of the year.
- For completely missing stop date, do not impute.
- If the stop date imputation leads to a stop date that is after the death date, then impute the stop date as the death date.

^{2 =} Impute the first of the month

^{3 =} Impute January 1 of the year

^{4 =} Impute January 1 of the stop year

Date: 24 March 2023 Page 46 of 53

If the stop date imputation leads to a stop date that is before the start date, then there is a data error and do not impute the stop date. (i.e. set the stop date as missing).

Imputation rules for partial or missing death dates:

If death year and month are available but day is missing:

- If mmyyyy for last contact date = mmyyyy for death date, set death date to the day after the last contact date.
- If mmyyyy for last contact date < mmyyyy for death date, set death date to the first day of the death month.
- If mmyyyy for last contact date > mmyyyy for death date, data error and do not impute.
- If both month and day are missing for death date or a death date is totally missing, do not impute.

Note that the last contact date refers to the last contact (i.e. a visit or an assessment) with patient instead of family members. Last contact date would be derived from the latest patient visit/assessment date.

Date: 24 March 2023 Page 47 of 53

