8.2.3.3 Vital Status

Vital status must be obtained for all subjects within the limits of local law. This includes subjects who may have discontinued study visits with or without withdrawing consent

and should include interrogation of public databases, if necessary. If deceased, the date and reported cause of death should be obtained.

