The subject's best response assignment will depend on the findings of both target and non-target disease and will also take into consideration the appearance of new lesions and confirmation of response. Confirmation of progressive disease is not required. Best overall response (BOR) will be based on all post-baseline disease assessments that occur prior to the initiation of subsequent anticancer treatment. At least 7 weeks from the first dose of IP must elapse without radiological disease progression to meet the minimum criteria for SD duration in order to assign a best overall response of SD. In general, subjects not classifiable under the RECIST 1.1

Date: 24 March 2023 Page 22 of 53

response categories due to inadequate data or early death will be classified as non-evaluable (NE) for BOR but will be counted in the denominator of all response rate calculations. The BOR will depend on the findings from MRI/CT scans. BOR per RECIST 1.1 has the following possible categories: complete response (CR), partial response (PR), stable disease (SD), progressive disease (PD) or not evaluable (NE). The rules for deriving the BOR are detailed in Appendix D.

Disease control rate (DCR)

DCR is defined as the **proportion** of subjects with a best overall response of confirmed response (CR/PR) or SD as per RECIST 1.1.

Duration of Response (DOR) per RECIST 1.1

DOR is defined as the time from the date of an initial objective response per RECIST 1.1 to the earlier of progressive disease per RECIST 1.1 or death for subjects with an objective response. **DOR** will be censored following the same censoring strategy as radiographic progression-free survival as detailed in Appendix B.

Objective Response (OR) per RECIST 1.1

OR is defined as best overall response of PR or CR per RECIST 1.1, confirmed by an assessment at least 4 weeks later. Subjects who do not experience a PR/CR or do not have any follow-up tumor assessments will be regarded as non-responders.

Objective Response Rate (ORR)

ORR is defined as the **proportion** of subjects with a best overall response of **confirmed** CR or PR per RECIST 1.1.

Overall Survival (OS)

OS is defined as the time from the start of treatment until event of death due to any cause. Subjects still alive will be censored at the date last known to be alive. If the date last known to be alive is after the date that triggers the analysis (i.e., the data cut-off date), the subject will be censored at the data cut-off date.

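### SAP Appendix A leaves a confirmed death with a year-only or missing date without an event time, so no SAP rule counts it in OS, and protocol 9.3.4 says otherwise

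*SAP*

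**What the plan says.** SAP Appendix A sorts death dates by how much of the date is known.

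- Day missing, last contact in the month of death: "If mmyyyy for last contact date = mmyyyy for death date, set death date to the day after the last contact date".
- Day missing, last contact in an earlier month: "set death date to the first day of the death month".
- Less than that known: "If both month and day are missing for death date or a death date is totally missing, do not impute".
- Conflicting months: "If mmyyyy for last contact date > mmyyyy for death date, data error and do not impute".

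SAP 5.3 defines the endpoint: "OS is defined as the time from the start of treatment until event of death due to any cause". Its censoring rule is: "Subjects still alive will be censored at the date last known to be alive". In Table 14-2 (Appendix B), a death without progression is an rPFS event on the date of death. The row for subjects with no post-baseline scan is limited to those alive or of unknown status. DOR borrows its censoring from the same appendix.

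Protocol 9.3.4 says that missing or incomplete dates critical to efficacy or safety will be imputed. It names the date of death as an example and leaves the detailed rules to the SAP. SAP 8.3 says partial death dates are imputed under Appendix A. SAP Section 10, on changes from the protocol, is silent on this. Protocol 8.2.3.3 requires vital status for every subject, including those who have stopped visits "and should include interrogation of public databases, if necessary", and asks for the date and cause of any death.

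**The concern.** A subject known to be dead, but without a month of death, meets neither OS rule: there is no date for the event, and the censoring rule is for the living. Because Appendix A forbids imputation outright, an analyst cannot fill the gap and still follow the plan. Someone would have to decide at analysis whether to leave the subject out or censor a known death. Both remove an event, and censoring also contradicts the OS definition.

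The subjects most exposed are those outside active follow-up, whose deaths are learned of from records rather than visits. At stake is an optimistic tilt in OS, and to a lesser extent in rPFS and DOR, produced by a choice that the plan leaves unstated.

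**Working it through.** The documents give no event count or precision figure for OS or rPFS, so there is no stated figure to reproduce. The check has two parts.

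**1. Which rule applies to a confirmed death without a usable date?**

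| Rule | Does it give a time? |
|---|---|
| Appendix A, day missing | No: it needs year and month |
| Appendix A, year only or nothing known | No: imputation is ruled out |
| OS event (SAP 5.3) | No: there is no death date |
| OS censoring (SAP 5.3) | No: the subject is not alive |
| Table 14-2, death without progression | No: there is no death date |
| Table 14-2, no post-baseline scan | No: it needs status alive or unknown |
| Table 14-2, no progression shown | Yes, by default: censored at the last scan, although the death row calls it an event |

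For rPFS, a subject with earlier progression keeps that event. A subject already censored for new therapy, or for two or more missed scans, is unaffected. OS is affected by every undated death.

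Appendix A is also uneven. Year-only start dates of adverse events and medications become the first-dose date or 1 January, and year-only stop dates become 31 December. Only the death date gets nothing.

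**2. How large is the effect on OS?**

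Input from the documents: n = 40 (Part 2 in the protocol; each Part 2 group in SAP 7.1). Assumptions: exponential OS with median m = 8, 12 or 18 months; administrative censoring uniform over 6 to 36 months; 1, 2 or 4 undated deaths picked at random among observed deaths; last contact 0 to 3 months before death; 4,000 simulated trials per setting, with all four treatments of the undated deaths applied to the same trials.

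Check of the simulation: true 12-month OS is 2^(−12/m), that is 35.4%, 50.0% and 63.0%. The complete-date estimates run 35.3–35.4%, 49.9–50.1% and 62.9–63.2%.

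Mean Kaplan-Meier 12-month OS (%):

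| Median | Undated | Complete dates | Dropped | Censored at last contact | Event at last contact + 1 day |
|---|---|---|---|---|---|
| 8 | 1 | 35.3 | 35.8 | 36.4 | 35.3 |
| 8 | 2 | 35.3 | 36.2 | 37.5 | 35.1 |
| 8 | 4 | 35.4 | 37.1 | 39.8 | 35.0 |
| 12 | 1 | 49.9 | 50.5 | 51.1 | 49.8 |
| 12 | 2 | 50.1 | 51.3 | 52.5 | 49.8 |
| 12 | 4 | 50.0 | 52.6 | 55.1 | 49.6 |
| 18 | 1 | 62.9 | 63.7 | 64.2 | 62.8 |
| 18 | 2 | 63.2 | 64.8 | 65.8 | 62.9 |
| 18 | 4 | 62.9 | 66.5 | 68.4 | 62.5 |

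Upward shift against complete dates:
- one undated death: 0.5 (35.8 − 35.3) to 1.3 (64.2 − 62.9) points;
- two: 0.9 (36.2 − 35.3) to 2.6 (65.8 − 63.2) points;
- four: 1.7 (37.1 − 35.4) to 5.5 (68.4 − 62.9) points.

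Counting the death the day after last contact stays within 0.4 points of the complete-date value in all nine settings.

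These are averages. With no censoring before 12 months, dropping a subject who died before the landmark changes S to 40S/39, a rise of S/39 (0.5/39 = 1.3 points at S = 50%). Dropping one who died after it changes S to (40S − 1)/39, a fall of (1 − S)/39. The mean shift was upward in every setting simulated, but a single landmark in a single trial can move either way if the subject is dropped.

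**The case against.** Declining to invent a date when even the month is unknown is a defensible instinct. Any imputed date brings its own error: up to a year early for a year-only date, or as early as the follow-up gap is long for a missing one. The close agreement above rests on gaps of 0 to 3 months; a lost subject found later in public records could have a much longer gap. This stands, and it is why the fix needs a sensitivity analysis. It does not justify losing the event, because the death itself is certain.

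Undated deaths should also be rare. Sites must seek the date, survival follow-up is every three months, SAP 5.1 has fatal serious adverse events collected during long-term follow-up, and data issues are to be resolved before lock. OS and rPFS are secondary and descriptive, no hypothesis is tested, and futility uses ORR. All of this stands and keeps the point minor.

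On the protocol conflict, 9.3.4 does delegate the detailed rules, and the SAP was written to Amendment 6, whose 9.3.4 text is not in hand. Delegating the method still does not cover a rule not to impute, and the two current documents disagree.

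Two stronger readings are tempting. A reader might take each undated death to move the curve by 1/40 = 2.5 points; that is one subject's weight, not the expected shift. A reader might also infer from "Last contact date would be derived from the latest patient visit/assessment date" that telephone contacts are ignored, so that an imputed death could precede a call with a living subject. Protocol 4.4.2 calls the three-monthly follow-up an assessment and includes telephone among its modes, so the documents do not support this. What Appendix A does exclude is contact with family members only.

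**Conclusion.** The point holds as a minor defect. Appendix A gives a confirmed death with a year-only or missing date no event time, no other rule supplies one for OS, and the result conflicts with protocol 9.3.4 without being listed in SAP Section 10. That the subject would be dropped or censored is an inference, since the SAP says neither. Under the assumptions shown, both raise 12-month OS on average, by about 0.5 to 1.3 points for one undated death in 40. The documents give no expected number; 0 to 2 subjects is an assumption, and four is a stress case. It would be wrong to treat OS and rPFS as equally affected: rPFS and DOR are touched only where the undated death has no earlier progression or censoring. No primary endpoint or stopping rule depends on this.

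**What to change.** 1. Query the site for the date first, including the conflicting-month case.
2. If it stays unresolved, count every confirmed death as an OS event, and as an rPFS or DOR event where Table 14-2 would count it. For a year-only date, use the later of 1 January of that year and the day after the subject was last known alive. For a wholly missing date, use the day after last known alive. Cap both at the data cut-off.
3. List these subjects and repeat OS over the possible date range. For example, the late end could be 31 December of the known year, or the date the death was learned of or the data cut-off if earlier.
4. Align Appendix A with protocol 9.3.4, or record the departure in SAP Section 10.

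The cost is two lines in Appendix A, one listing and one sensitivity run, all before lock. The downside is that imputed times are early, by up to a year for year-only dates or by the length of the follow-up gap for missing ones.
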